Immunodeficiencies of interest	Comorbidity	Defined as ≥1 ICD-10 diagnosis code for immunodeficiency. Complete list in ANNEX 5. LIST OF DIAGNOSIS CODES FOR SELECT IMMUNODEFICIENCIES OF INTEREST.
Prior use of corticosteroids	Medication history	Defined as ≥1 prescription dispensing of a corticosteroid (as identified by ATC code[s]) in the 12 months prior to the index tofacitinib dispensing. Complete list in ANNEX 4. LIST OF ATC CODES FOR COMEDICATIONS OF INTEREST
Prior use of statins	Medication history	Defined as ≥1 prescription dispensing of a statin (as identified by ATC code[s]) in the 12 months prior to the index tofacitinib dispensing. Complete list in ANNEX 4. LIST OF ATC CODES FOR COMEDICATIONS OF INTEREST.

Table 3. Operational definitions of study variables in Système National des Données de Santé

Variable	Role	Operational definition
Prior use of any biologic	Medication history	Defined as ≥1 prescription dispensing of a biologic (as identified by ATC code[s]) in the 12 months prior to the index tofacitinib dispensing. Complete list in ANNEX 7. LIST OF ATC CODES FOR MEDICATIONS OF INTEREST TO AVOID WHILE TAKING TOFACITINIB.
Prior use of conventional synthetic DMARDs (csDMARDs)/ Immunomodulators	Medication history	Defined as ≥1 prescription dispensing of a csDMARD/ Immunomodulators (as identified by ATC code[s]) in the 12 months prior to the index tofacitinib dispensing. Complete list in ANNEX 7. LIST OF ATC CODES FOR MEDICATIONS OF INTEREST TO AVOID WHILE TAKING TOFACITINIB.
Prior use of MTX	Medication history	Defined as ≥1 prescription dispensing of MTX (as identified by ATC code L04AX03) in the 12 months prior to the index tofacitinib dispensing.
Prior use of anti-TB therapy	Medication history	Defined as ≥1 prescription dispensing of anti-TB therapy (as identified by ATC code[s]) in the 12 months prior to the index tofacitinib dispensing.
Prior vaccination	Medication history	Defined as ≥1 procedure code, ≥1 ICD-10 code and/or ≥1 reimbursed prescription (as identified by ATC code[s]) for a vaccination, overall and stratified by live and non-live vaccinations (if available) in the 12 months prior to the index tofacitinib dispensing. Complete list in ANNEX 4. LIST OF ATC CODES FOR COMEDICATIONS OF INTEREST.

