ANNEX 4. LIST OF ATC CODES FOR COMEDICATIONS OF INTEREST

All codes will be reviewed and updated prior to study initiation.

Class of drug	Drug	ATC code
Corticosteroids	Aldosterone	H02AA01
	Fludrocortisone	H02AA02
	Desoxycortone	H02AA03
	Betamethasone	H02AB01
	Dexamethasone	H02AB02
	Fluocortolone	H02AB03
	Methylprednisolone	H02AB04
	Paramethasone	H02AB05
	Prednisolone	H02AB06
	Prednisone	H02AB07
	Triamcinolone	H02AB08
	Hydrocortisone	H02AB09 (D07XA01 topical
		use)
	Cortisone	H02AB10
	Prednylidene	H02AB11
	Rimexolone	H02AB12
	Deflazacort	H02AB13
	Cloprednol	H02AB14
	Meprednisone	H02AB15
	Cortivazol	H02AB17
	Methylprednisolone, combinations	H02BX01
	Trilostane	H02CA01
	Phenylbutazone and corticosteroids	M01BA01
	Dipyrocetyl and corticosteroids	M01BA02
	Acetylsalicylic acid and corticosteroids	M01BA03
Methotrexate	Methotrexate	L04AX03
Statins	Atorvastatin	C10AA05
	Atorvastatin and acetylsalicylic acid	C10BX08
	Atorvastatin and amlodipine	C10BX03
	Atorvastatin and ezetimibe	C10BA05
	Atorvastatin and perindopril	C10BX15
	Atorvastatin, acetylsalicylic acid and perindopril	C10BX12
	Atorvastatin, acetylsalicylic acid and ramipril	C10BX06
	Atorvastatin, amlodipine and perindopril	C10BX11
	Cerivastatin	C10AA06
	Fluvastatin	C10AA04
	Gemigliptin and rosuvastatin	A10BH52
	Imipenem and cilastatin	J01DH51
	Lovastatin	C10AA02
	Lovastatin and nicotinic acid	C10BA01
	Nystatin	A07AA02, D01AA01, G01AA01
	Nystatin, combinations	G01AA51
	Pentostatin	L01XX08
	Pitavastatin	C10AA08
	Pravastatin	C10AA03
	Pravastatin and acetylsalicylic acid	C10BX02

PFIZER CONFIDENTIAL

Class of drug	Drug	ATC code
	Pravastatin and fenofibrate	C10BA03
	Rosuvastatin	C10AA07
	Rosuvastatin and acetylsalicylic acid	C10BX05
	Rosuvastatin and amlodipine	C10BX09
	Rosuvastatin and ezetimibe	C10BA06
	Rosuvastatin and valsartan	C10BX10
	Rosuvastatin, amlodipine and lisinopril	C10BX07
	Rosuvastatin, amlodipine and perindopril	C10BX14
	Rosuvastatin, perindopril and indapamide	C10BX13
	Simvastatin	C10AA01
	Simvastatin and acetylsalicylic acid	C10BX01
	Simvastatin and ezetimibe	C10BA02
	Simvastatin and fenofibrate	C10BA04
	Simvastatin, acetylsalicylic acid and ramipril	C10BX04
	Sitagliptin and simvastatin	A10BH51
Vaccinations	Anthrax antigen	J07AC01
	Brucella antigen	J07AD01
	Cholera, inactivated, whole cell	J07AE01
	Cholera, live attenuated	J07AE02
	Cholera, combinations with typhoid vaccine,	J07AE51
	inactivated, whole cell	
	Diphtheria toxoid	J07AF01
	Haemophilus influenzae B, purified antigen	J07AG01

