ANNEX 7. LIST OF ATC CODES FOR MEDICATIONS OF INTEREST TO AVOID WHILE TAKING TOFACITINIB

All codes will be verified and updated prior to study initiation.

Class of drug	Drug	ATC code
Biologics	Abatacept	L04AA24
	Adalimumab	L04AB04
	Anakinra	L04AC03
	Certolizumab	L04AB05
	Etanercept	L04AB01
	Golimumab	L04AB06
	Infliximab	L04AB02
	Ixekizumab	L04AC13
	Rituximab	L01XC02
	Secukinumab	L04AC10
	Sarilumab	L04AC14
	Tocilizumab	L04AC07
	Ustekinumab	L04AC05
	Vedolizumab	L04AA33
Conventional synthetic DMARDS	Gold preparation (sodium aurothiomalate)	M01CB01
(csDMARD)	Gold preparation (sodium aurotiosulfate)	M01CB02
	Gold preparation (auranofin)	M01CB03
	Gold preparation (aurothioglucose)	M01CB04
	Gold preparation (aurotioprol)	M01CB05
	Hydroxychloroquine	P01BA02
	Leflunomide	L04AA13
	Olsalazine	A07EC03
	Penicillamine	M01CC01
	Sulfasalazine	A07EC01
Targeted synthetic DMARDS	Apremilast	L04AA32
•	Baricitinib	L04AA37
	Upadacitinib	L04AA44
	Filgotinib	L04AA45
Other DMARDS	Balsalazide	A07EC04
	Olsalazine	A07EC03
	Sulfasalazinea ^a	A07EC01
Selected potent	6-Mercaptopurine	L01BB02
immunosuppressant	Azathioprinea ^a	L04AX01
	Cyclosporinea ^a	L04AD01
	Tacrolimus	L04AD02

a Denotes that the medicine may also be classified as a csDMARD. csDMARD = conventional synthetic DMARDS

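### Prior csDMARD/immunomodulator use is read from an annex that omits methotrexate, so a patient whose only prior agent was methotrexate is scored as having none

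*Protocol*

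**What the plan says.** In Table 3 of Section 9.3.1, the row for prior use of csDMARDs/immunomodulators reads: "Defined as ≥1 prescription dispensing of a csDMARD/ Immunomodulators (as identified by ATC code[s]) in the 12 months prior" to the index dispensing. It then sends the reader to one code list: "Complete list in ANNEX 7. LIST OF ATC CODES FOR MEDICATIONS OF INTEREST TO AVOID WHILE TAKING TOFACITINIB". The row names no class within that annex and states no exclusion.

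Annex 7 has five drug classes: biologics, conventional synthetic DMARDs, targeted synthetic DMARDs, other DMARDs and selected potent immunosuppressants. The conventional synthetic class holds the gold preparations, "Hydroxychloroquine", leflunomide, olsalazine, penicillamine and "Sulfasalazine". Azathioprine, cyclosporine, tacrolimus and "6-Mercaptopurine" are under potent immunosuppressants. Footnote a, attached to azathioprine, cyclosporine and the second sulfasalazine entry, says: "Denotes that the medicine may also be classified as a csDMARD".

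Methotrexate is not in Annex 7. Annex 4 carries it as a class of its own: "Methotrexate Methotrexate L04AX03". The Table 3 row after the csDMARD row reports prior MTX use separately, over the same 12 months and with that ATC code.

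**The concern.** The cross-reference borrows a list built for another purpose. Annex 7 collects drugs that should not be combined with tofacitinib. Section 7 describes tofacitinib being given with methotrexate in RA and PsA, so methotrexate has no place on such a list. A variable meant to capture all prior csDMARD use therefore misses one, and nothing in the row warns of it.

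Prior medication use by indication is part of primary objective 1. Section 7 describes the RA and PsA approvals as following inadequate response or intolerance to DMARD therapy. A reader of the report will look to a row with this label for treatment history before tofacitinib, and the figure there would be lower than the label implies.

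The second problem is reproducibility. The row does not say which Annex 7 classes make it up, so two programmers could follow the text faithfully and report different proportions, particularly in UC if azathioprine or 6-mercaptopurine is the prior agent.

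**Working it through.** No sample size, power or test figure depends on this variable, so there is no stated number to reproduce. The check sets Table 3 against Annexes 4 and 7 and asks how each drug is scored under each plausible reading of the row.

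- Reading A: only the Annex 7 csDMARD class counts.
- Reading B: A plus the drugs carrying footnote a.
- Reading C: B plus the rest of the potent immunosuppressants, taken as the immunomodulators.
- Reading D: the whole of Annex 7.

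| Only prior agent | A | B | C | D |
|---|---|---|---|---|
| Gold, hydroxychloroquine, leflunomide, olsalazine, penicillamine, sulfasalazine | yes | yes | yes | yes |
| Azathioprine, cyclosporine | no | yes | yes | yes |
| 6-mercaptopurine, tacrolimus | no | no | yes | yes |
| Biologics, targeted synthetic DMARDs, balsalazide | no | no | no | yes |
| Methotrexate | no | no | no | no |

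1. **Methotrexate.** It is scored as no under every reading. This part of the finding does not depend on resolving the ambiguity.

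2. **Direction.** Adding methotrexate to any fixed list can only move patients from no to yes, so its omission can only lower the proportion. Reading D would push the other way by counting biologics as csDMARDs, but the label of the row rules that reading out.

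3. **Which classes count.** Readings A to C are all compatible with the text. The annex is also uneven: sulfasalazine carries footnote a and is listed in the csDMARD class as well, whereas azathioprine and cyclosporine carry the same footnote and are not. 6-mercaptopurine and tacrolimus carry no footnote, and no class is named immunomodulators.

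4. **Can the reader repair it from the MTX row?** Let *a* be the proportion in the csDMARD row and *m* the proportion in the MTX row. The proportion with either lies between max(*a*, *m*) and min(1, *a* + *m*). Its position in that interval depends on the overlap, which Table 3 does not ask for. Section 9.4 allows only aggregated data in communications, so a reader cannot recover it.

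5. **Size.** The shortfall is P(MTX in the prior 12 months) × P(no counted drug, given MTX). The protocol gives neither factor. Purely as an assumption, 30% to 50% for the first and 50% to 80% for the second give 0.30 × 0.5 = 0.15 to 0.50 × 0.8 = 0.40, or 15 to 40 percentage points. These inputs are not in the documents, and the result only shows how the formula behaves.

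**The case against.** The strongest reply is that methotrexate is not lost. It has its own row with the same window, and reporting it apart may be deliberate. The study also holds patient-level claims, so a count of any csDMARD including MTX needs no new data. All of that is true, but the csDMARD row does not say that methotrexate is excluded. Table 3 does state exclusions where it means them, as for malignancy excluding NMSC and for VTE risk factors other than CV or malignancy factors. The fact that the union is easy to compute is a reason to ask for it.

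A second reply is that the lists are provisional: Section 9.3.1 allows refinement in the SAP, and Annex 7 says its codes will be verified. This carries weight for the class ambiguity. It carries less for methotrexate, because checking the codes on a list of drugs to avoid would rightly find methotrexate absent. The fault is in the cross-reference.

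Two stronger readings are tempting and should be resisted:

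- **Patients on the main csDMARDs generally count as untreated.** They do not. Hydroxychloroquine, leflunomide and sulfasalazine are listed and counted.
- **An azathioprine-only or 6-mercaptopurine-only UC patient is definitely scored as having no prior agent.** The protocol does not say so. Both drugs are in the annex that the row cites, and the row's mention of immunomodulators supports inclusion at least as well as exclusion. This is an ambiguity and not a stated rule.

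Nor does the error reach the adherence results. Off-label status rests on diagnosis codes, alternative therapy means biologics, and no comparative test uses the prior-csDMARD row.

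**Conclusion.** The point holds in a limited form. As written, the row scores a methotrexate-only patient as having no prior csDMARD, and the primary objective 1 proportion is understated to that extent. That methotrexate is a csDMARD is general pharmacological knowledge; neither annex labels it so. The direction for methotrexate is certain, but the magnitude cannot be derived from the protocol.

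The treatment of azathioprine, cyclosporine, 6-mercaptopurine and tacrolimus is unsettled and needs a decision. A reader might infer that a low figure in this row would show use outside the approved line of therapy. The protocol contains no such outcome, so the consequence is a misleading descriptive figure. It should be corrected because the correction is cheap and the row serves a primary objective, but the adherence and comparative analyses are unaffected.

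**What to change.** Give the row its own code list: the Annex 7 csDMARD class plus methotrexate (L04AX03) and the two footnoted drugs, azathioprine (L04AX01) and cyclosporine (L04AD01). State whether 6-mercaptopurine (L01BB02) and tacrolimus (L04AD02) count as immunomodulators for this variable.

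If separate reporting of methotrexate is intended, relabel the row as other than MTX and add a row for any csDMARD including MTX. The class decision is needed in either case.

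Leave Annex 7 itself unchanged. Table 3 relies on it for prior biologic use, for the alternative-therapy component of the adherence outcomes and for the incompatible-medication outcomes. Adding methotrexate to it would also sit badly with the combination use described in Section 7.

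The cost is a short code list and one changed cross-reference in Table 3, plus one extra table row under the alternative. No additional data are needed.

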Concomitant use of a contraindicated potent immunosuppressants	Comedication	Defined as ≥30 overlapping days' supply of a tofacitinib prescription dispensing and a prescription dispensing for a contraindicated potent immunosuppressants (as identified by ATC code[s]) during the follow-up period. Days of supply in SNDS will be approximated by reimbursed package size and per recommended posology. Duration of tofacitinib therapy defined in Section 9.3.2.
Concomitant use of MTX	Comedication	Defined as ≥30 overlapping days' supply of a tofacitinib prescription dispensing and a prescription dispensing for MTX during the follow-up period.
Concomitant use of a corticosteroid	Comedication	Defined as ≥30 overlapping days' supply of a tofacitinib prescription dispensing and a prescription dispensing for a corticosteroid (as identified by ATC code[s]) during the follow-up period.
Concomitant use of anti-TB therapy	Comedication	Defined as ≥30 overlapping days' supply of a tofacitinib prescription dispensing and a prescription dispensing for anti-TB therapy (as identified by ATC code[s]) during the follow-up period.

Table 3. Operational definitions of study variables in Système National des Données de Santé

Variable	Role	Operational definition
Primary Objective 2: Pr	escribers' adherenc	e to the tofacitinib aRMMs
		per indication and duration of use
Duration of tofacitinib	Outcome:	Defined in Section 9.3.2. Assessed during the follow-up
therapy	Adherence to	period.
	recommended	
	posology	
ADD	Outcome:	Defined in Section 9.3.3. Assessed during the follow-up
	Adherence to	period.
	recommended	
	posology	
A patient with an	Outcome:	Among RA/PsA patients is defined as 0 ICD-10 diagnosis
ADD of >11 mg	Adherence to	code for UC during baseline or follow-up period and an
during any of the 8-	recommended	ADD of >11 mg during any of the 8-week intervals.
week intervals and no	posology	
evidence of a		
diagnosis for UC		
A patient with an	Outcome:	Among UC patients, is defined as ≥ 1 prescription dispensing
ADD of ≥15 mg in	Adherence to	for a biologic (as identified by ATC codes) prior to the index
Weeks 17-24, Weeks	recommended	tofacitinib dispensing and an ADD ≥15 mg in any of the
25-32, Weeks 33-40 or	posology	intervals: Weeks 17-24, Weeks 25-32, Weeks 33-40 or
Weeks 41-48 of		Weeks 41-48 of follow-up.
follow-up and with		Complete list of biologics in ANNEX 7. LIST OF ATC
evidence of a		CODES FOR MEDICATIONS OF INTEREST TO AVOID
diagnosis for UC but		WHILE TAKING TOFACITINIB

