no use of an		Note: This definition will miss those who have one 10 mg
alternative therapy		BID prescription and the remaining prescriptions are 5 mg
(i.e., biologic) prior to		BID.
tofacitinib initiation		
A patient who has	Outcome:	Among UC patients, is defined as ≥ 1 prescription dispensing
known VTE, CV or	Adherence to	for a biologic (as identified by ATC codes) prior to the index
malignancy risk	recommended	tofacitinib dispensing and an ADD >10 mg in any of the
factors with an ADD	posology	intervals: Weeks 17-24, Weeks 25-32, Weeks 33-40 or
of >10 mg in Weeks		Weeks 41-48 of follow-up and ≥1 VTE, CV or malignancy
17-24, Weeks 25-32,		risk factors from baseline to Week 16.
Weeks 33-40 or		
Weeks 41-48 of		An ADD \geq 15 mg in the definition above will be used in a
follow-up and with		sensitivity analysis.
evidence of a		
diagnosis for UC but		
no use of an		
alternative therapy		
(i.e., biologic) prior to		
tofacitinib initiation		

Adherence to patient screening and laboratory monitoring prior to and during tofacitinib treatment

The following recommended screenings and monitoring will be assessed in the following time frames:

- In the 30 days prior to and including the day of tofacitinib initiation;
- In the 31 to 60 days prior to tofacitinib initiation;

Table 3. Operational definitions of study variables in Système National des Données de Santé

Donnees de Sante			Donnees	
	Variable	Role		Operational definition

- In the 61 to 90 days prior to tofacitinib initiation; and
- In the 91 to 180 days prior to tofacitinib initiation;

For patients with at least 6 months of tofacitinib therapy (duration of tofacitinib therapy defined in Section 9.3.2):

- In the 60 days after the day of tofacitinib initiation;
- In the 61 to 120 days after tofacitinib initiation; and
- In the 121 to 180 days after to facitini binitiation.

For patients with 12 months of tofacitinib therapy (duration of tofacitinib therapy defined in Section 9.3.2):

- In the 181 to 240 days after tofacitinib initiation;
- In the 241 to 300 days after to facitinib initiation; and
- In the 301 to 360 days after to facitinib initiation.

For analyses, 1 month will be defined as 30 days and 1 year will be defined as 360 days.

List of laboratory codes in ANNEX 10. LIST OF LABORATORY TEST CODES.

List of laboratory codes	III THI TILL TO. LIDT	OF EMBORITORY TEST CODES.
Creatinine (serum or	Outcome:	Defined as ≥1 procedure code or ≥1 ICD-10 diagnosis code

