Initiating tofacitinib with ≥1 VTE risk factor(s)	Outcome: changes in use in patients with VTE risk factors	Defined as ≥1 VTE risk factor(s) (as listed and defined above) identified in the 12 months prior to the index tofacitinib dispensing.
Initiating tofacitinib with ≥1 VTE risk factors other than CV or malignancy risk factors	Outcome: changes in use in patients with VTE risk factors	The same definition as above but only limited to VTE risk factors other than CV or malignancy risk factors.
VTE risk factor scores	Outcome: changes in use in patients with VTE risk factors	Calculated as the sum of the number of VTE risk factors (as listed and defined above) identified in the 12 months prior to the index tofacitinib dispensing. Weighting of VTE risk factors may be considered as a sensitivity analysis to reflect the potential different
Number of UC patients with: ≥1 VTE risk factor; no prior alternative therapy (i.e., biologic); and an ADD >10 mg in Weeks 17-24, Weeks 25-32, Weeks 33-40 or Weeks 41-48 of follow-up	Outcome: changes in use in patients with VTE risk factors	importance of each risk factor. Defined as an UC patient meeting all of the following criteria: ≥1 VTE risk factor(s) (as listed and defined above) 12 months prior to the index tofacitinib prescription dispensing; 0 prescription medication dispensing for a biologic (as identified by ATC codes) in the 12 months prior to the index tofacitinib prescription dispensing; and an ADD of >10 mg in any of the intervals: Weeks 17-24, Weeks 25-32, Weeks 33-40 and Weeks 41-48 of follow-up (ADD defined in Section 9.3.3). Complete list of biologics in ANNEX 7. LIST OF ATC CODES FOR MEDICATIONS OF INTEREST TO AVOID WHILE TAKING TOFACITINIB.
Assessment of VTE risk; Section 9.3.2)	factors while receiving	tofacitinib therapy (duration of tofacitinib therapy defined in
VTE	Outcome: changes in use in patients with VTE risk factors	Defined as ≥1 ICD-10 diagnosis code for VTE while receiving tofacitinib therapy. List of VTE codes in ANNEX 12. LIST OF DIAGNOSIS CODES FOR VTE

Table 3. Operational definitions of study variables in Système National des Données de Santé

Variable	Role	Operational definition
Surgery, major	Outcome: changes in use in patients with VTE risk factors	Defined as ≥1 procedure code for a major surgery while receiving tofacitinib therapy.
MI	Outcome: changes in use in patients with VTE risk factors	Defined as ≥1 ICD-10 diagnosis code for an MI while receiving tofacitinib therapy.

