9.7.2.4.1. Patients with venous thromboembolism risk factors

To describe changes in the utilisation of tofacitinib, this analysis will be stratified by the VTE reporting periods 1, 2 and 3.

The proportion of patients with one or more risk factors for VTE, identified prior to tofacitinib initiation, will be described and tabulated overall and by individual VTE risk factor (e.g., prior VTE and recent MI).

Logistic regression analyses will be used to calculate odds ratios along with their corresponding 95% confidence intervals and p values to formally compare the proportion of patients with VTE risk factors across VTE reporting periods 1, 2 and 3.

To enhance statistical power in detecting changes, a composite score for the VTE risk factors will also be generated by summing the individual VTE risk factors. Linear regression analyses will be employed to compare the VTE composite score across the VTE reporting periods. In addition to the summed composite score, the same analysis using a composite score weighting the risk factors may be considered in an exploratory fashion (weights will be developed and described in the SAP). Regression coefficients with their 95% confidence intervals and p values will be generated.

The proportion of patients diagnosed with UC, one or more VTE risk factors identified prior to tofacitinib initiation and no use of alternative therapy (i.e., biologic) prior to tofacitinib initiation whose ADD in Week 17 through Week 24, Week 25 through Week 32, Week 33 through Week 40 or Week 41 through Week 48 was >10 mg will be described and tabulated.

The proportion of patients who discontinue or continue to facitinib after developing one or more VTE risk factors while taking to facitinib will be described separately.

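### Two UC posology outcomes named for patients with no prior biologic are defined as having at least one, so they count the wrong patients

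*Protocol*

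**What the plan says.** Table 3 in Protocol Section 9.3.1 has two UC rows with the role of adherence to recommended posology.

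- **Row 1** is named for UC patients with an ADD of at least 15 mg in any 8-week interval from Weeks 17-24 to Weeks 41-48 and no biologic before starting tofacitinib.
- **Row 2** is named for UC patients with a VTE, CV or malignancy risk factor, an ADD above 10 mg in any of the same intervals, and again no prior biologic. A sensitivity analysis repeats it at 15 mg or more.

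The names are broken over several table lines, but the condition can be read in both: "diagnosis for UC but" is followed by the words for no use of an alternative therapy, and then "i.e., biologic) prior to" tofacitinib initiation.

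The definition beside each name begins "Among UC patients, is defined as ≥ 1 prescription dispensing" and continues "for a biologic (as identified by ATC codes) prior to the index" dispensing. In row 2 this is joined to the dose condition: "tofacitinib dispensing and an ADD >10 mg in any of the" intervals listed.

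A third row, in the VTE block of the same table, covers UC patients with a VTE risk factor, no prior biologic and an ADD above 10 mg. It is defined with "0 prescription medication dispensing for a biologic (as identified by ATC codes) in the 12 months prior to the index tofacitinib prescription dispensing". Section 9.7.2.4.1 analyses that outcome as "no use of alternative therapy (i.e., biologic) prior to tofacitinib initiation whose ADD in Week 17" and later intervals exceeded 10 mg.

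**The concern.** The operational definition is what a programmer implements, and in both rows it is the complement of the group in the name. Section 9.9.1.1 explains that the absence of a prior biologic stands in for departure from the SmPC condition on suitable alternatives, because claims data cannot show suitability. Under that proxy the patients of interest are those on a high maintenance ADD who had not tried a biologic. The rows as written collect those who had.

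Section 9.7.2.1 commits to reporting all variables with this role, and they serve Primary Objective 2. The study is meant to inform a regulator whether the risk minimisation materials work. A table headed as showing no prior biologic would contain only patients with one.

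**Working it through.** No stated figure is at issue, so the check is a comparison of texts followed by a short illustration.

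**Step 1. Name against definition**

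| Table 3 row | Prior biologics in the name | Prior biologics in the definition |
|---|---|---|
| UC, ADD at least 15 mg (posology block) | 0 | at least 1 |
| UC with VTE, CV or malignancy risk factor, ADD above 10 mg (posology block) | 0 | at least 1 |
| UC with VTE risk factor, ADD above 10 mg (VTE block) | 0 | 0 in 12 months |

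The wording is complete and identical in the first two rows, so text extraction is not a plausible cause.

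**Step 2. Which side is the slip**

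- Table 3 defines prior use of any biologic as at least one dispensing in the 12 months before index. The two UC rows therefore carry the condition of the opposite variable.
- The no-prior-use outcomes for patients aged 65 and older at initiation, for CV risk factors and for malignancy risk factors all require zero dispensings.
- Among patients who turn 65 on treatment, the continuation outcome without prior alternatives requires zero dispensings and the one with prior alternatives requires at least one.
- Section 9.7.2.4.1 and the proxy in Section 9.9.1.1 agree with zero.

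Nothing in the protocol explains or corrects the two exceptions.

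**Step 3. Reach of the error**

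- Row 1 has no correctly defined counterpart. The VTE row is restricted to patients with VTE risk factors, and the JAKi-referral row to patients with CV or malignancy risk factors.
- Row 2's sensitivity analysis refers back to the same definition and inherits the error.
- The VTE row is sound. The JAKi-referral row does not select on prior biologic; it is stratified by it.

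**Step 4. Illustration of size**

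Let b be the share with a prior biologic among UC patients who already meet the ADD condition (and, in row 2, the risk-factor condition). The protocol does not give b, so the values are assumptions. Per 100 such patients:

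- counted by the name: 100 × (1 − b)
- counted by the definition: 100 × b

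| b | Name | Definition |
|---|---|---|
| 0.3 | 70 | 30 |
| 0.5 | 50 | 50 |
| 0.6 | 40 | 60 |
| 0.7 | 30 | 70 |
| 0.9 | 10 | 90 |

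The totals agree only at b = 0.5, and even there no patient is in both sets.

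**The case against.** The contradiction itself is hard to dispute. The case on the other side concerns its weight.

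1. **The intent is recoverable.** Section 9.3.1 calls the algorithms preliminary and open to refinement in the SAP, and the rest of the protocol points to zero. That makes this a drafting slip, not a deliberate choice. But reversing an inclusion condition goes beyond refining a code list, and Section 9.7 says major changes to primary endpoint definitions would be reflected in a protocol amendment.

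2. **The rows are not the only posology measures for UC.** This stands. Duration and ADD per 8-week interval are also reported, and the VTE and JAKi-referral rows give part of what row 2 is meant to show. The affected rows are descriptive only: neither the regressions in Sections 9.7.2.4 and 9.7.2.5 nor the study size in Section 9.5 uses them. However, stratifying ADD by prior biologic is optional and depends on sample size (Section 9.3.3), and row 1 is not reproduced elsewhere.

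3. **The look-back is already bounded.** The two rows say only that the biologic precedes index. Section 9.3.1 sets the baseline and follow-up periods as the default window, and Section 9.2.3 fixes baseline at 12 months. Some age-65 rows omit the window too. This largely stands: an explicit window is a tidy-up, not a separate fault.

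4. **Size and direction are unknown.** This also stands. A 60% to 90% share has no source in the protocol; a share below 50% would make the written definition undercount.

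**Conclusion.** The point holds. Two posology-adherence outcomes for UC are defined as the complement of what they are named. The swap is complete among UC patients who meet the ADD condition (and, for row 2, the risk-factor condition); patients below the ADD threshold are unaffected. For an assumed prior-biologic share of 60% to 90%, the rows would report 60 to 90 per 100 instead of 10 to 40, but the true share, and so the direction of the numerical error, cannot be taken from the protocol. That the wrong patients are counted does not depend on the share. Adherent and non-adherent are used here only in the sense of the protocol's own proxy, whose misclassification Section 9.9.1.1 acknowledges. Because these rows feed a primary-objective table and row 1 has no sound counterpart, they should be corrected before programming.

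**What to change.** In both UC rows of Table 3, replace the requirement of at least one biologic dispensing before index with zero biologic dispensings in the 12 months before index. Zero agrees with the row names, the VTE row, Section 9.7.2.4.1 and the proxy in Section 9.9.1.1. The 12-month window comes from the VTE row and the baseline period in Section 9.2.3; Section 9.7.2.4.1 gives no window. Report patients with at least one prior biologic as a separate, labelled stratum, so that both groups are visible. Row 2's sensitivity analysis is then corrected automatically.

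The cost is two table-cell edits and the matching lines of the programming specification. No additional data are needed, and study size, the regression analyses and the other outcomes do not change. The edit reconciles the protocol with itself and takes no position on any dosing recommendation.
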